## **13.2 Analysis of Overall Tolerability**

The CGI is a 3-item observer-rated scale that measures illness severity, global improvement or change and therapeutic response. A modified version of the CGI will be used in this trial to assess “illness” instead of “mental” illness. For CGI Items 1 and 2, a table of frequencies as well as a table of summary statistics will be produced, broken down by treatment group and visit. Item 3 will only be tabulated in frequency tables. The two dimensions of the item, ‘Therapeutic effect’ and ‘Side effects’, will be tabulated separately and overall.

For all CGI Items, a score of 0 (‘Not assessed’) will be treated as missing data and will thus be excluded from the computation of summary statistics. The scale does not support the computation of a summary (total) score.

A table of frequencies will be prepared for the Investigator’s Tolerability Assessment at Visit 3.

Pairwise treatment group comparisons will be performed for CGI Items 1 and 2, for the dimensions of Item 3 assessed separately as well as for the Investigator’s Tolerability Assessment using Wilcoxon-Mann-Whitney U-tests. Comparisons for CGI between treatment groups will be provided for Visit 3 and for Visit5/EOT.

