13.2.2 Visit 1 / Baseline Visit / Randomization

Baseline Prior to Start of Treatment

- Verify Informed Consent was obtained
- Verify Demographics/Medical History
- Repeat Urine/Serum Pregnancy Test (Urine samples can be collected at the Randomization Visit in order to obtain results quickly while the patient is in the clinic and not delay randomization)
- Physical examination
- Vital signs
- Clinical laboratory tests
- PK blood sample pre-dose
- Spirometry
- Randomization
- Concomitant medications/therapies
- AEs
- CGI (Item 1 only)
- SF-36 questionnaire

Start of Treatment

Following activities will be performed:

- Train patient on L-CsA **CCI** use, drug storage, and inhalation technique
- IMP Administration. Supervise first inhalation for proper use of the nebulizer and for tolerability issues.
- Verify patient is familiar with drug administration and use of nebulizer device
- Emphasize importance of adherence to IMP
- Emphasize importance of adherence to usual medications as taken prior to participating in the trial
- Spirometry: (1 hour \pm 20 minutes after completion of dosing with IMP)
- PK blood samples directly after end of inhalation, 15, 30, and 45 minutes (+/- 5 min), and 1, 1.5, 2, and 4 hours (+/- 15 min.) after end of inhalation
- Local IMP tolerability

Prior to release from clinic, study drug and the nebulizer system for home use will be dispensed to each patient. Patient will receive full IMP supply for the 12 weeks treatment period.

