14.2.3.3 Measures of Overall Tolerability

For the measures of over-all tolerability identified in [Section 12.1.5](#), descriptive statistics will be presented by visit (see [Section 14.2.1](#)). Pairwise treatment group comparisons will be performed for applicable visits using exact Wilcoxon-Mann-Whitney U-tests.

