## 6 CHANGES TO STUDY PROTOCOL

The planned analysis will be performed according to the study protocol, its amendments and this statistical analysis plan. If there are contradictions between the study protocol or its amendments and this statistical analysis plan, the analysis will be performed according to this analysis plan. Any deviation from the planned analysis has to be described in the CSR.

The differences between study protocol and statistical analysis plan are summarized in the following table:

Change	Clinical Study Protocol (CSP)	In the Statistical Analysis Plan Will be changed to:
Wording in CSP	Major Protocol Deviation Minor Protocol Deviation	Important Protocol Deviation Non-Important Protocol Deviation

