## 8.2 Randomization and Stratification

At the Baseline visit (V1), after all inclusion and exclusion criteria have been fully evaluated, eligible patients will be assigned to one of the three treatment groups at a ratio of 1:1:1 by means of block randomization.

No stratification will be performed.

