## **9.2 Sample Size Considerations**

This is a Phase IIa study in a rare indication, with very limited availability of eligible patients and a purely descriptive statistical concept. Accordingly, the sample size for the study was established based on considerations of feasibility rather than on power calculations.

A total of 24 patients (3 arms with 8 patients in each) are planned to be randomized.

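### CGI Item 1 (illness severity) is compared between arms without its Visit 1 rating, and the SAP leaves open whether the Wilcoxon-Mann-Whitney p-values are exact

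*SAP*

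**What the plan says.** **Collection.** Protocol 13.2.2 lists "CGI (Item 1 only" among the assessments made before the first dose at Visit 1. Protocol 13.2.3 has Items 1 to 3 rated at Visits 2 to 5. Protocol 12.1.9 says the CGI cannot be rated at a remote visit.

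**Role.** SAP 8.3 places the CGI under overall tolerability within the primary endpoints (first 4 weeks). SAP 8.4 and 14.1 extend it to 12 weeks as a secondary assessment.

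**Test.** SAP 13.2: "Pairwise treatment group comparisons will be performed for CGI Items 1 and 2, for the dimensions of Item 3 assessed separately", together with the investigator's tolerability assessment, by Wilcoxon-Mann-Whitney tests. The CGI comparisons are made at Visit 3 and Visit 5/EoT. No change score or baseline term is named for Item 1. A score of 0 counts as missing. Protocol 14.2.3.3 specifies the same pairwise comparisons "using exact Wilcoxon-Mann-Whitney U-tests"; the SAP does not carry over the first word.

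**Precedence.** SAP 6 says that where the two documents contradict each other, "the analysis will be performed according to this analysis plan". Its table of differences has one entry, the renaming of major and minor protocol deviations.

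**Size and allocation.** SAP 9.2: "A total of 24 patients (3 arms with 8 patients in each) are planned to be randomized", a number set "based on considerations of feasibility rather than on power calculations". SAP 8.2: "eligible patients will be assigned to one of the three treatment groups at a ratio of 1:1:1 by means of block randomization" and "No stratification will be performed".

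**The concern.** Item 2 (global change) and Item 3 (therapeutic and side effects) are already judged against the patient's starting point. Item 1 is not: it records how ill the patient is now. A difference in Item 1 at Week 4 mixes what happened on treatment with how ill each arm was at entry. With 8 per arm and no stratification, sizeable differences at entry are common. The information needed to remove them is collected and then left out of the test. The SAP does use baseline as a covariate for spirometry and the SF-36 (15.1, 15.2).

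The second matter is how p-values are obtained. CGI and tolerability ratings are coarse, and at 8 per arm they will be heavily tied. Exact and asymptotic p-values can then differ enough to change how a result is described. A programmer working from the SAP alone could take either.

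**Working it through.** **Inputs from the documents.** n = 8 per arm (SAP 9.2), no stratification (SAP 8.2), Item 1 at Visit 1 (Protocol 13.2.2). The plan's total reproduces: 3 x 8 = 24. No power, effect size, SD or correlation is given, so there is no power figure to reproduce. Everything below that involves a correlation r between the Visit 1 and later Item 1 scores, a 7-point scale or a 1 SD effect is an assumption.

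**1. Chance imbalance at entry.** The SE of the difference between two arm means is SD x sqrt(2/8) = 0.5 SD.
- One pair differing by more than 0.5 SD: P(|Z| > 1) = 0.32.
- One pair differing by more than 1 SD: P(|Z| > 2) = 0.05.
- At least one of the three pairs, by simulation: 0.58 for 0.5 SD or more, 0.11 for 1 SD or more.

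**2. What each use of baseline does to variance.** Relative to the unadjusted score, the variance is 2(1 - r) for a change score and 1 - r² for a baseline-adjusted score. Normal-theory power for a true 1 SD difference, 8 v 8, two-sided 0.05:

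| r | change / unadjusted variance | adjusted / unadjusted variance | power unadjusted | power change | power adjusted |
|---|---|---|---|---|---|
| 0.3 | 1.40 | 0.91 | 0.52 | 0.39 | 0.55 |
| 0.5 | 1.00 | 0.75 | 0.52 | 0.52 | 0.64 |
| 0.7 | 0.60 | 0.51 | 0.52 | 0.73 | 0.80 |
| 0.8 | 0.40 | 0.36 | 0.52 | 0.88 | 0.91 |

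**3. The same on a tied ordinal scale.** The formula above ignores ties and the small sample, so its levels are optimistic. Simulated on a 7-point scale with a 1 SD shift:
- Unadjusted Wilcoxon: about 39-42%.
- Rank ANCOVA on the Visit 1 score: 43, 44, 51, 63 and 74% at r = 0, 0.3, 0.5, 0.7 and 0.8, with type I error about 5-6%.
- Change score at r = 0.3: 28%, against 39% unadjusted.

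With exact p-values throughout (1,500 replicates), the unadjusted score gives 35-37%. Baseline-adjusted ranks give 46, 51, 57 and 69% at r = 0.5, 0.6, 0.7 and 0.8, and the change score gives 34, 42, 47 and 57%. The gain from adjustment therefore does not depend on an asymptotic p-value.

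**4. Exact against asymptotic.** Take a two-category outcome split 8/0 in one arm and 4/4 in the other.
- Exact: 2 x C(8,4)/C(16,4) = 2 x 70/1820 = 0.077.
- Asymptotic: the rank sum is 52 against an expected 68. The tie-corrected variance is (64/12) x (17 - 1776/240) = 51.2. So z = 16/7.155 = 2.24 and p = 0.025, or 0.030 with continuity correction.

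That table is a deliberately sparse case. Over three assumed ordinal distributions under no effect, 8 v 8, type I error was 0.013-0.034 exact and 0.040-0.053 asymptotic. The two versions fell on opposite sides of 0.05 in about 1-3% of datasets.

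**The case against.** **The SAP does not contradict the protocol on exactness.** A reader might infer that the SAP has replaced the exact test with an asymptotic one. It has not said so. An exact Wilcoxon-Mann-Whitney test is still a Wilcoxon-Mann-Whitney test, the SAP's precedence applies only to contradictions, and SAP 6 also says the analysis follows the protocol. This stands: the fault is silence that leaves the method open, not a substitution.

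**Type I error is not the problem.** It is tempting to argue that an asymptotic test would be anti-conservative at this size. On average it is not materially so, at most about 0.053 in the settings tried. The exact test is the conservative one with ties.

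**The unadjusted comparison is not biased.** A reader might say that baseline severity distorts the treatment effect. Randomization makes the comparison right in expectation; what is lost is precision and protection against chance imbalance in this one sample. SAP 9.1 also calls for change from baseline to be tabulated for repeated outcomes, so imbalance will be visible. The tabulation does not alter the test, however.

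**Little hangs on the p-value.** Protocol 14 makes every p-value descriptive, and Item 1 is one component among many. Protocol 14.2.3.3 names no baseline adjustment either, so that half is a design improvement and not a protocol-SAP discrepancy. This limits the weight of the point. It does not explain leaving out a covariate that is already collected.

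**Change from baseline is not a free gain.** This is correct: at r = 0.3 it loses about as much power as it gains at higher correlations. It is why the remedy is adjustment and not subtraction.

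**Conclusion.** The point holds at moderate weight. SAP 13.2 tests a severity rating between arms of 8 without using the pre-treatment rating of the same item. The comparison is unbiased in expectation but less precise than it could be, and it is exposed to chance imbalance: at least one pair of arms is 0.5 SD or more apart at entry with probability about 0.58. In simulation, baseline-adjusted ranks matched the unadjusted test at r = 0 and gained roughly 10 points of power at r = 0.5 and 20 or more at r = 0.7. These gains rest on an assumed 7-point scale, a 1 SD effect and assumed correlations; the documents supply none of them.

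The missing word on exactness is certain as a matter of text and small in effect. It matters mainly for sparse tables, and more so if remote visits or unassessed scores take the arms below 8.

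**What to change.** In SAP 13.2:

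1. For CGI Item 1, compare arms at Visit 3 and Visit 5/EoT by a baseline-adjusted rank analysis with the Visit 1 score as covariate, for example rank ANCOVA. Add a permutation p-value if an exact-type test is wanted; this also deals with the slight excess over 5% seen in simulation. Do not use a simple change score as the tested quantity.
2. Leave Items 2 and 3 as scored.
3. Restore exact for all remaining Wilcoxon-Mann-Whitney tests, in line with Protocol 14.2.3.3. If an asymptotic test is intended, list and justify it in SAP 6.
4. Say how a patient with no usable Visit 1 Item 1 score is handled, since that patient would drop out of the adjusted comparison.

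The cost is SAP wording and a few lines of programming, with no new data. The one small downside is that exact tests are somewhat conservative with tied scores.

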14 STATISTICS

This section presents an overview of the planned analyses. Final analyses are not limited to the summaries described herein. The Statistical Analysis Plan (SAP) will provide a detailed description of the planned statistical analyses and data summaries, and will be finalized before database lock or any unblinding for this study. If circumstances arise during the clinical trial that make these analyses inappropriate or if improved methods become available, the SAP may be revised. If discrepancies exist between the text of the statistical analysis as planned in the protocol and the final SAP, the final SAP will define the planned analysis of record. Reasons for such discrepancies will be described in the final Clinical Study Report (CSR).

This is a Phase IIa, prospective, multicenter, randomized, placebo-controlled trial with a fixed sample size design.

All analyses will be exploratory, and hence any p-values will be interpreted descriptively without adjustment.

Data will be listed by patient and treatment group.

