14.2 Statistical and Analytical Methods

14.2.1 Descriptive Statistics

The data recorded in the case report forms will be summarized as appropriate, per treatment group and for the total group, using the following descriptive measures:

- All continuous assessments will be summarized using descriptive statistics (i.e., N, mean, standard deviation, median, lower quartile (Q1), upper quartile (Q3), minimum, and maximum).
- All categorical assessments will be summarized by time point, as applicable, using frequency counts and percentages.
- Discrete ordinal or metric data will be summarized as continuous data, but a tabulation of categories may be included additionally depending on the number of categories.

For all measures analyzed descriptively (i. e., measures to characterize the treatment groups and their baseline status, efficacy, and safety outcomes), tabulations comparing the treatment groups will be prepared. For outcomes measured more than once, the analyses will include tabulations of the measured values by visit as well as an analysis of change from baseline. Where provided, all confidence intervals will be two-sided 95% confidence intervals.

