## **9.3 Type I Error Considerations**

Not applicable.

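### Overall tolerability is part of the primary endpoint, but its only planned between-arm inference is a Wilcoxon test at 8 v 8, with no effect estimate or confidence interval

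*SAP*

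**What the plan says.** The primary endpoint in SAP 8.3 is tolerability and safety over the first 4 weeks. Overall tolerability is listed under it through two instruments, the CGI and the Investigator's Tolerability Assessment.

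SAP 13.2 plans frequency tables by arm for these instruments and summary statistics for CGI Items 1 and 2. For comparing arms it names one method, applied to CGI Items 1 and 2, to the two dimensions of Item 3, "as well as for the Investigator’s Tolerability Assessment using Wilcoxon-Mann-Whitney U-tests". Protocol 14.2.3.3 plans the same comparison with one more word: "Pairwise treatment group comparisons will be performed for applicable visits using exact Wilcoxon-Mann-Whitney U-tests". Neither section names an effect measure or an interval.

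The inferential frame is deliberately light. Protocol 14 says that "any p-values will be interpreted descriptively without adjustment". SAP 9.3 answers the type I error question with "Not applicable", and SAP 13.5 gives no working hypothesis. On size, SAP 9.2 says that "the sample size for the study was established based on considerations of feasibility rather than on power calculations", and "A total of 24 patients (3 arms with 8 patients in each) are planned to be randomized".

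Elsewhere the SAP plans interval-based comparisons: Wilson intervals for local tolerability (13.1) and TEAEs (13.3.1), and 95% intervals for PK (14.2), spirometry (15.1) and SF-36 (15.2). Sections 13.1 and 13.3.1 also add a pooled L-CsA v placebo comparison; 13.2 does not.

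**The concern.** The trial's purpose is to describe how each dose is tolerated relative to placebo. A p-value conveys neither the size of a difference nor its precision. At 8 per arm, a p-value of 0.3 or 0.6 fits both no difference and a large one. The exploratory efficacy outcomes receive an estimate with its uncertainty, while this primary component receives a test alone.

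What is at stake is the tolerability statement in the study report. Without an interval, nothing in the planned output for this component shows how much worsening has not been excluded.

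**Working it through.** **Inputs from the documents.** There are 8 patients per arm and 24 in total (SAP 9.2), allocated 1:1:1 (SAP 8.2). The Investigator's Tolerability Assessment is a five-point rating (Protocol 12.1.5). Intervals, where given, are two-sided 95% (Protocol 14.2.1).

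**Assumptions, because the documents give no figure.** These are a two-sided 0.05 level, worsening of 0.5 to 2 SD, and the placebo rating distributions shown below.

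**1. The plan's own figure.** 3 × 8 = 24, which agrees. No power, detectable difference or alpha is stated, so there is nothing further to reproduce.

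**2. What the test needs at 8 v 8.** Under the exact null distribution without ties, two-sided p ≤ 0.05 requires U ≤ 13 (actual size 0.0499). The observed probability of a worse rating must then be at least 1 − 13/64 = 0.797.

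**3. Power for a normal shift without ties (simulation, 40,000 runs).**

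| Worsening (SD) | 8 v 8 | 6 v 6 | Pooled 16 v 8 |
|---|---|---|---|
| 0.5 | 15% | 10% | 18% |
| 1.0 | 44% | 30% | 56% |
| 1.1 | 51% | 35% | 63% |
| 1.5 | 77% | 59% | 88% |
| 2.0 | 95% | 83% | 99% |

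The 8 v 8 column crosses 50% at about 1.1 SD. The 6 v 6 column is shown because the CGI cannot be done remotely (Protocol 12.1.9), Visit 3 may be remote (13.2.7), and randomized patients are not replaced (9.3.3).

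**4. Power on a five-point scale with ties, 8 v 8.** Assume placebo ratings of 40/30/15/10/5% from very good to poor, and shift the underlying normal scale by d. The cumulative probabilities become Φ(c_k − d), where c_k are the placebo cut-points. Full enumeration with the exact tie-conditional p-value gives:
- 0.5 SD (moderate or poor rises from 15% to 30%): power 12%
- 1 SD (15% to 49%): 39%
- 1.1 SD (15% to 53%): 46%
- 1.5 SD (15% to 68%): 72%
- 2 SD (15% to 83%): 92%

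A proportional-odds model with placebo 50/30/10/7/3% gives a similar picture. A cumulative odds ratio of 5 (moderate or poor from 10% to 36%) has power 34%, and an odds ratio of 8 has 53%.

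**5. What an interval would show.** Let θ = P(L-CsA rated worse) + 0.5 P(tie). Before ties, the null standard error is √[(n + m + 1)/(12nm)] = √[17/(12 × 64)] = 0.149. With no observed difference, the 95% interval is about 0.5 ± 1.96 × 0.149 = 0.21 to 0.79.

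**6. A hypothetical data set.** Ratings from very good to poor are 4/3/1/0/0 on placebo and 3/1/0/2/2 on L-CsA. Half the treated patients are rated moderate or poor, against none on placebo.
- θ = (3 × 2 + 1 × 5.5 + 2 × 8 + 2 × 8)/64 = 43.5/64 = 0.68.
- The exact two-sided p is 0.22.
- A large-sample interval from the placement variances (SE 0.141) is 0.68 ± 1.96 × 0.141, about 0.40 to 0.96.

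The planned test would report only 0.22. The interval would show that a large excess of worse ratings is not excluded.

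**The case against.** The strongest reply is that the p-value does not stand alone. With 8 patients on a five-point scale, a frequency table by arm displays essentially all the data, and SAP 9.1 promises tabulations comparing the groups for every measure. This stands. A reader might infer that the p-value is the only comparative information, and the documents do not support that. What the tables lack is a summary of the difference with its uncertainty.

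A second reply is that the misreading is hypothetical. A reader might infer that the sponsor will conclude tolerability from p > 0.05. No such rule is written, no alpha is set, and p-values are descriptive. That lowers the risk. It also weakens the case for making a test the sole inferential output.

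Third, a reader might infer that a non-significant result is likely under any real harm. It is not: power at 8 v 8 is 77% at 1.5 SD and 95% at 2 SD without ties.

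Fourth, overall tolerability is not unique. Laboratory values, vital signs and physical examination are also primary components, and SAP 13.3.2 gives them no between-arm interval. The introduction to SAP 13 also describes the primary assessments as safety and local tolerability. However, it refers to 8.3, which includes overall tolerability, and 13.2 sits within that chapter. Unlike 13.3.2, it does plan between-arm inference.

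Fifth, the missing pooled contrast is not a departure from the protocol. Protocol 14.2.3.2 confines pooling to the adverse-event section, so adding it to 13.2 would be an extension.

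**Conclusion.** The concern holds as a reporting gap worth closing. For a component of the primary endpoint, the plan names a test at 8 v 8 and no estimate or interval, although it plans intervals for most other compared outcomes. At an assumed two-sided 0.05, the test more often misses than detects a worsening up to about 1.1 SD, or a cumulative odds ratio of about 7 to 8. These figures rest on assumed effect sizes and placebo distributions. The absence of an estimate and interval does not depend on them.

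There is also one unlisted discrepancy. The protocol specifies the exact test; SAP 13.2 drops that word, and the table of changes in SAP 6 does not record it. The SAP governs, and with heavy ties at n = 8 the choice can matter.

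The point does not extend to every CGI measure. Items 1 and 2 and the therapeutic-effect dimension rate illness severity, improvement and benefit, so they should not carry a harm conclusion.

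**What to change.** In SAP 13.2, for the Investigator's Tolerability Assessment and the side-effects dimension of CGI Item 3, at Visit 3 and EoT:

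- Report θ = P(L-CsA rated worse than placebo) + 0.5 P(tie) with a two-sided 95% confidence interval, for each dose v placebo.
- Add pooled L-CsA v placebo as a supportive contrast matching 13.1 and 13.3.1, labelled as an addition to the protocol.
- Name an interval method that remains valid with ties and complete separation at n = 8, such as a score-type or permutation-based interval. Simple variance-based intervals can collapse there.
- Keep the U-test p-value as secondary and restore the word exact.
- State that a non-significant p-value is not evidence of comparable tolerability.

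The other CGI measures may carry the same estimate descriptively, without supporting a harm conclusion.

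The cost is SAP wording and 2 measures × 2 visits × 3 contrasts = 12 intervals, from data already collected. The intervals will be wide and will make the tolerability statement look less favourable. They add no power, and they do not address rating by investigators, who are not blinded (Protocol 8.3.1).
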